Clinical investigation plan

**C20-691
(EX-MKTG-121)**

**The comparative clinical performance of two daily
disposable toric contact lenses**

A multi-centre study

**A clinical evaluation for
CooperVision Inc.**

[figure not shown]
**Principal Investigator
[name]**

May 2021

Contents

Document control	3
Study summary	
Section 1. Overview	5
1.1 Background	5
1.2 Personnel	5
1.3 Study objectives	6
1.4 Study design	6
1.5 Statistical considerations	6
1.6 Risk analysis	7
Section 2. Resources	8
2.1 Subject selection	8
2.2 Subject discontinuation	9
2.3 Safety parameters, adverse events and concurrent illnesses	10
2.4 Study termination	10
2.5 Protocol deviations	10
2.6 Study resources	10
2.7 Study control	11
2.8 Documentation	12
2.9 Data collection and analysis	12
2.10 Study completion	12
2.11 Confidentiality	12
2.12 Study monitoring	12
Section 3. Subject management	14
3.1 Visit scheduling	14
3.2 Visit conduct	14
3.3 Monitoring subject compliance	22
3.4 Missing, unused and spurious data	22
Section 4. Study co-ordination	23
4.1 Document processing	23
4.2 Disclosure	23
4.3 Personnel	23

Study summary

This open-label, randomised, bilateral, crossover multi-centre study will compare the clinical performance and subjective acceptance of the MyDay Toric and DAILIES TOTAL1 Toric daily disposable soft toric contact lenses, when used on a daily wear, daily disposable basis. Up to 55 subjects will be enrolled and will wear each lens brand for one week in random sequence. The following will be assessed throughout the study: ocular physiology, lens fit, lens surface, visual acuity and subjective response. A study summary is shown in Table 1.

V st	Procedures
Int a	Informed consent taken Explanation of study procedures and subject instructions Ocular, medical and contact lens histories [REDACTED] Biomicroscopy Fitting of study lenses part 1 (from fitting bank) [REDACTED] Lens fit Fitting of study lenses part 2 (from fitting bank) [REDACTED] Lens fit Order study lenses Changes to general and ocular health and medications Biomicroscopy Fitting of study lenses part 1 [REDACTED] Lens fit Subjective scores Issue study lenses Changes to general and ocular health and medications [REDACTED] Subjective scores Retrieval of unused lenses [REDACTED] Lens fit Removal of lenses Biomicroscopy Fitting of study lenses part 2 [REDACTED] Lens fit Subjective scores Issue second study lenses Changes to general and ocular health and medications [REDACTED] Subjective scores Retrieval of unused lenses [REDACTED] Lens fit Removal of lenses [REDACTED] Payment processed
D spending 1	
Follow-up 1 / D spending 2 (6-11 days from D sp 1)	
Follow-up 2 (6-11 days from D sp 2)	

Table 1: Study summary.

Section 1. Overview

1.1 Background

This project seeks to compare the clinical performance of the MyDay Toric (CooperVision Inc.) and DAILIES Total1 Toric (Alcon Inc.) daily disposable soft toric contact lenses.

1.2 Personnel

This work will be managed by Eurolens Research, The University of Manchester, under the general direction of [name] PhD MCOptom FAAO FBCLA. The Principal Investigator for the work is [name]. Approximately 19 subjects will be enrolled by Eurolens Research. Subjects will also be seen at a minimum of three external optometric practices, who will enrol approximately 36 subjects between them.

In addition to the university, the investigators are all UK-based optometrists registered to practice optometry with the General Optical Council:

1.3 Study objectives

This study aims to compare the clinical performance of the MyDay Toric and DAILIES Total1 Toric daily disposable toric contact lenses.

1.4 Study outcome measures

The primary outcome measure for this study is subjective handling on lens removal. Secondary measures are lens fit parameters and biomicroscopy scores [REDACTED]

1.5 Study design

This will be a multi-centre, randomised, open-label, crossover, bilateral study, controlled by cross-comparison. Up to 55 subjects will use each lens type for a week in random sequence. Follow-up visits for each lens will be performed after one week of wear. Lenses will be worn on a daily wear, daily disposable wear schedule.

1.6 Statistical considerations

The principal hypothesis to be tested in this work is that handling on lens removal scores for the two lenses are the same. Secondary hypotheses are that [REDACTED]

[REDACTED] lens fit parameters and biomicroscopy scores are also the same.

[REDACTED] such, these will

be compared using linear regression models or other parametric methods. Subjective preferences will be compared using chi-squared tests. Lens fit data are expected to be ordinal data and assessed with non-parametric approaches. Deviations from this statistical plan will be discussed in the final report. Deviations may be necessary due to differences between the actual data distribution compared with the anticipated data distribution.

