1.6.1 Power analysis

Power analysis using data from a previous study for subjective scores for lens removal on a 0-10 scale indicated that 50 subjects are required to complete the study to provide 90% power, assuming a standard deviation of 1.5 units for intra-subject differences and a meaningful difference of 0.7 units¹. To allow for discontinuations, up to 55 subjects will be enrolled.

¹ Based on the work of Papas et al. (2011).

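### Does naming linear regression for a crossover comparison forfeit the 90% power that was calculated on within-subject differences?

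*Combined protocol and SAP*

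**What the plan says.** Section 1.5 describes a randomised crossover: "Up to 55 subjects will use each lens type for a week in random sequence". The two amendments raise maximum enrolment to 65 and then 70. The first states that the target of 50 completers is unchanged, and the second does not alter it.

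Section 1.4 sets the endpoint: "The primary outcome measure for this study is subjective handling on lens removal". Section 1.6 states the null hypothesis that "handling on lens removal scores for the two lenses are the same".

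Section 1.6.1 aims for 90% power with 50 completers. It reaches that number by "assuming a standard deviation of 1.5 units for intra-subject differences and a meaningful difference of 0.7 units". This is a paired calculation.

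On method, section 1.6 says that certain outcomes will "be compared using linear regression models or other parametric methods". The words that define those outcomes are redacted. The visible text gives preferences to chi-squared tests and lens fit to non-parametric methods, so the removal score is most naturally read as belonging to the regression sentence. That is an inference. No visible text mentions a subject, period or sequence term, and none says that a subject's two scores will be treated as independent.

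**The concern.** Each completer scores both lenses, so 50 completers give 100 scores. Someone who took linear regression at its simplest would regress the 100 scores on lens type. With complete pairs the estimated lens difference would be the same as in a paired analysis, but its standard error would not. Differences between people in how they use a 0–10 scale would enter the error term, whereas the sample-size calculation excludes them.

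If a subject's two scores are positively correlated, as is plausible for one person rating the same task twice, the standard error is then too large. The confidence interval is too wide, the test is conservative, and part of the 90% power is lost. Since the sample size depends on pairing and the visible method does not mention it, the two sections look mismatched.

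**Working it through.** **Inputs.** Section 1.6.1 gives the SD of within-subject differences (1.5), the difference of interest (0.7), 50 completers and 90% power. The visible text states no significance level. Two-sided 5% is assumed, which suits a null hypothesis of equality. The within-subject correlation ρ is not given, so a range is assumed.

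**Step 1: reproduce the plan's figure.**
- Normal approximation: n = [1.5 × (1.960 + 1.282) / 0.7]² = 48.3, rounded up to 49.
- Exact paired t-test: 51 subjects (90.5% power).
- At n = 50: SE = 1.5/√50 = 0.212 and 0.7/0.212 = 3.30. Power is 91.0% by normal approximation, 89.9% by paired t, and 89.9% with the n − 2 degrees of freedom of a two-period crossover analysis.
- An unpaired two-group formula with SD 1.5 gives 2 × 48.3 = 96.5, or 97 per group. One-sided 5% gives 40 to 41.

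The stated 50 is therefore a paired, two-sided 5% figure.

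**Step 2: the analysis that ignores subject.**
- SD of a single score: s = 1.5/√[2(1 − ρ)].
- SE from regression on lens alone: s × √(2/50) = 0.2s, which is the paired SE multiplied by 1/√(1 − ρ).
- CI half-width, which is also the rejection threshold: t(0.975, 98 df) × SE, with t = 1.984.
- Power: the probability that the mean difference, distributed N(0.7, 0.212²), exceeds the threshold.

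For example, at ρ = 0.5: s = 1.50, SE = 0.300, threshold = 0.595, and power = Φ[(0.7 − 0.595)/0.212] = 69%.

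| Assumed ρ | SE | 95% CI half-width | Power | Actual type I error |
|---|---|---|---|---|
| 0 | 0.212 | 0.42 | 91% | 4.7% |
| 0.2 | 0.237 | 0.47 | 86% | 2.7% |
| 0.3 | 0.254 | 0.50 | 82% | 1.8% |
| 0.5 | 0.300 | 0.60 | 69% | 0.5% |
| 0.7 | 0.387 | 0.77 | 37% | below 0.1% |

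Simulation with 40,000 trials per case agrees to within one percentage point of power (38% at ρ = 0.7). In the same simulations the paired test holds at about 90% for every ρ. Its half-width is about 0.43.

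**Step 3: compare with the wording.** A linear regression may carry a subject effect. A paired t-test and a linear mixed model are parametric methods. All of these lie within the class that section 1.6 names, and the paired test is the one that the sample size was built on. The losses in the table need a further choice, to leave subject out, which appears nowhere in the visible text.

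**The case for a change.** The strongest case for a change is that the wording admits analyses with very different properties, and that choosing between them after seeing the data would not count as a deviation, because each fits the text. Section 3.4 allows partial datasets where appropriate. A paired t-test drops a subject with one period and a mixed model keeps that subject, so the estimate could depend on the choice. One sentence would settle it at almost no cost.

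Part of this stands. The visible text does not fix the model, and it names no period or sequence term. Three things limit its weight.

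- The introductory words are redacted, so the plan cannot be faulted for omitting what may be written there.
- With a non-negative correlation, ignoring subject makes the test conservative. The risk is lost precision, and the sponsor would bear it; a false claim of a lens difference does not become more likely.
- Among the sensible within-subject analyses little turns on the choice. Power with 50 completers is 89.9% with either n − 1 or n − 2 degrees of freedom. Enrolment was raised because many subjects were found ineligible, according to the second amendment at the initial visit. The visible text first collects a removal score at Follow-up 1 (section 3.2.4), so those subjects add no one-period data. The documents do not say how many others might stop after one period.

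**Conclusion.** No change to the plan follows. The power figures for a regression without a subject term are correct as arithmetic: 86%, 69% and 37% at assumed correlations of 0.2, 0.5 and 0.7. They describe an analysis that the plan does not specify. The named class already contains the within-subject methods that deliver the stated power (89.9% by paired t, 91.0% by normal approximation, at two-sided 5%), and the sample size of 50 completers is sound.

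The crossover in section 1.5 and the within-subject SD in section 1.6.1 tell an analyst that the pairing has to be used. Writing that down would make the text more complete, but it would move the analysis to nothing outside what section 1.6 already allows. This conclusion rests on two readings: that the removal score falls under the regression sentence, and that whoever sized the trial on within-subject differences will analyse it that way. If subject were in fact ignored, the losses in the table would apply.

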2.1.1 Subject withdrawal and replacement

This study includes four clinical visits. Once the study consent form is signed, the subject is considered to be enrolled on the study. Subjects who have signed the consent form, but who have not completed the initial visit will usually be replaced. All subject data will be included in the final analyses unless there are strong grounds for exclusion; such grounds will be detailed in the final report.

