2.1.3 Inclusion criteria

Subjects will only be eligible for the study if:

1. They are aged between 18 and 40 years and have capacity to volunteer.
2. They understand their rights as a research subject and are willing and able to sign a Statement of Informed Consent.
3. They are willing and able to follow the protocol.
4. They currently wear soft contact lenses or have done so in the past two years.
5. They have a spherical component of their contact lens prescription between Plano to - 6.00DS (inclusive).
6. They have a cylindrical component of their contact lens prescription between -0.75DC and -2.50DC (inclusive).
7. They can be satisfactorily fitted with the study lens types.
8. At dispensing, they can attain at least 6/12 distance high contrast visual acuity in each eye with the study lenses within the available power range.

9. They are willing to comply with the wear schedule (at least five days per week and for at least eight hours per day).
10. They own a wearable pair of spectacles.
11. They agree not to participate in other clinical research while enrolled on this study.

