2.7 Study control

This study is controlled by cross-comparison. Bias will be minimised by randomising the order of assessment.

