2	
Number of subjects
 
The original protocol stated that up to 55 subjects should be enrolled, as the power calculation is based on 50 subjects completing the study.
 
As a result of a much higher number of ineligible subjects than expected, up to 65 subjects will now be enrolled. The intended number of subjects to complete remains 50.
 
As the lens SKU range is now increased, any subject who was originally ineligible owing to the required lens not being available, can now be re-enrolled and, if they wish to re-enrol, will be treated as a new subject (i.e. they will reconsent and re-attend the initial visit and so on).
 
Subjects found ineligible for other reasons will not be re-enrolled.
																											

Table 2: Changes to protocol C20-691 (version 1.0)

Document approved by:

Protocol amendment

Study title: The comparative clinical performance of two daily disposable toric contact lenses

The table below lists the changes to be implemented in this work:

New revision no.	Section/s to be Amended and details
1	
Inclusion criterion 1 originally read 'They are aged between 18 and 40 years old and have capacity to volunteer'.
 
Now amended to 'They are at least 18 years old and have capacity to volunteer'

2	
Number of subjects
 
The original protocol stated that up to 55 subjects should be enrolled, as the power calculation is based on 50 subjects completing the study. Protocol amendment 1 increased the maximum number to 65. In order to avoid falling short of the required number of completed subjects, owing to a high rate of subjects being found ineligible at the initial visit, the maximum number of subjects to be enrolled is increased to 70.

Table 1: Changes to protocol C20-691 (version 1.0)

Document approved by:

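### Must the crossover analysis of the removal score name a period term?

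*Combined protocol and SAP*

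**What the plan says.** Section 1.5 (Study design) describes the crossover: "Up to 55 subjects will use each lens type for a week in random sequence". Section 2.7 (Study control) gives the protection against order effects: "Bias will be minimised by randomising the order of assessment". Section 1.6 (Statistical considerations) sets the primary hypothesis as equality of the removal-handling scores for the two lenses. After a redacted stretch it says that certain measures will "be compared using linear regression models or other parametric methods". No lens, period, sequence or subject term is visible. Section 1.6.1 (Power analysis) asks for 50 completers for 90% power, "assuming a standard deviation of 1.5 units for intra-subject differences and a meaningful difference of 0.7 units".

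**The concern.** Each subject scores removal twice, about a week apart. If scores drift between weeks, for instance through practice, the drift enters each subject's lens difference with a sign that depends on which lens came first. An analysis by lens alone then has two weaknesses. With equal orders, the drift inflates the error variance and costs power. With unequal orders among completers, it also moves the estimate.

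Unequal orders are possible. Section 2.1.1 says "Subjects who have signed the consent form, but who have not completed the initial visit will usually be replaced", and the second protocol amendment raises the enrolment cap to 70 "owing to a high rate of subjects being found ineligible at the initial visit". The visible text does not say whether a replacement takes the vacated place in the randomisation list. The permission for other parametric methods would also admit a plain paired test. So the plan appears to randomise order without committing to use it, and to leave the primary model open in an open-label trial.

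**Working it through.** **Inputs.** From section 1.6.1: SD of within-subject differences 1.5, difference 0.7, 50 completers, 90% power. Assumed, because the visible text gives no value: two-sided 0.05, 1:1 allocation to the two orders, and a period effect p of 0.3 or 0.5 units.

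**The plan's own figure.** Normal approximation: n = (1.5 × (1.960 + 1.282) / 0.7)² = 48.2, so 49. Paired t with 49 df: SE = 1.5/√50 = 0.212, noncentrality 0.7/0.212 = 3.30, power 89.9%. The stated 50 and 90% reproduce to rounding.

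**Model.** The lens difference for a subject is 0.7 + p or 0.7 − p, according to order, plus error with SD 1.5. Let n1 and n2 be the completers in each order.

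- *Lens only (paired t, 49 df).* The estimate shifts by p(n1 − n2)/50. The sum of squares divided by 1.5² is noncentral chi-square with noncentrality 4p²n1n2/(50 × 1.5²). At 25/25 this is 2.0 for p = 0.3 and 5.6 for p = 0.5.
- *Lens + period (48 df).* SE = 0.5 × 1.5 × √(1/n1 + 1/n2), which is 0.212 at 25/25 and 0.214 at 28/22. The result does not depend on p.

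**Cost of the term if there is no period effect.** Power at 25/25 is 89.85% with the term and 89.88% without. At 28/22 it is 89.4%, a loss of 0.5 point. The average loss is 0.65 point over unrestricted randomisation, and 0.2 point for a balanced 35/35 list that loses 20 of 70 at random.

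**Effect of leaving it out if there is one.**

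| Setting | Lens only, p = 0.3 | Lens only, p = 0.5 | With period |
|---|---|---|---|
| Power, 25/25 | 89.1% | 87.8% | 89.9% |
| Average power, unrestricted | 88.7% | 86.6% | 89.2% |
| Average power, balanced list losing 20 | 89.0% | 87.4% | 89.7% |

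Average type I error of the lens-only test is 5.0% under unrestricted randomisation, and 4.7% (p = 0.3) or 4.2% (p = 0.5) for the balanced list. The gain from the term at p = 0.3 is therefore 89.2 − 88.7 = 0.5 point or 89.7 − 89.0 = 0.7 point.

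**Break-even.** The two analyses have equal average power at p of about 0.22 units (unrestricted), 0.14 units (balanced list losing 20) and 0.05 units (exactly 25/25). Below these values the lens-only test is slightly better.

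**If the 1.5 already contains a period effect.** It may, if it is the raw SD of differences from the previous study. The stated 89.9% then stands for a lens-only analysis at 25/25, and adjustment would raise power to 91.0% (p = 0.3) or 92.9% (p = 0.5).

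**The case for a change.** The best case for acting is that the sponsor runs one trial, not the average of many. At a realised 28/22 split the lens-only estimate shifts by 0.3 × 6/50 = 0.04 units or 0.5 × 6/50 = 0.06 units. Power is then 85.7% or 81.3% if the shift opposes the true difference, and 91.9% or 92.5% if it favours it, against 89.4% adjusted. A split at least that uneven has probability 48% under unrestricted randomisation and 18.5% for the balanced list losing 20. One sentence in the plan would remove this dependence and fix the model before the data are seen.

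The arithmetic stands, and so does the remark that the visible text names no terms. Three things limit its weight:

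- Type I error at 28/22 is 4.9% or 4.7%, so the test stays valid there. What is at risk is some power, in either direction.
- The effect must be assumed, and 0.5 units is 0.5/0.7 = 71% of the difference the plan calls meaningful. The plan points to something smaller. Section 2.1.3 admits subjects on the condition "They currently wear soft contact lenses or have done so in the past two years", section 3.2.2 provides instruction in removal where needed, and Table 3 places the first follow-up score 6 to 11 days after dispensing.
- The 48% needs unrestricted randomisation, which no passage states. Section 3.2.2 refers to a randomisation table, next to a redaction.

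**Conclusion.** No change is needed. The missing model terms are at most an unstated detail, and the redacted words beside the sentence may already supply them; text lost to redaction cannot be counted as absent from the plan. The visible text rules nothing out. Regression is the method named first, the power calculation already rests on within-subject differences, and an analyst of a randomised two-period crossover would ordinarily fit lens and period with subject as the block. An analyst who ran the plain paired test instead would still have a valid comparison, with average type I error at or below 5.0%. At an assumed period effect of 0.3 units that choice costs about 0.5 to 0.7 point of average power. At 0.5 units it costs 89.2 − 86.6 = 2.6 points or 89.7 − 87.4 = 2.3 points. Below about 0.14 to 0.22 units it costs nothing. The statement in section 2.7 that randomising the order limits bias is correct, and the 50 completers remain adequate under either model. These sizes rest on two-sided 0.05, 1:1 allocation, losses unrelated to order, and an SD of 1.5 that excludes period unless stated otherwise. The sponsor may choose to confirm the terms and report completers by order, but the soundness of the result does not depend on it.

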1.6.1 Power analysis

Power analysis using data from a previous study for subjective scores for lens removal on a 0-10 scale indicated that 50 subjects are required to complete the study to provide 90% power, assuming a standard deviation of 1.5 units for intra-subject differences and a meaningful difference of 0.7 units¹. To allow for discontinuations, up to 55 subjects will be enrolled.

¹ Based on the work of Papas et al. (2011).

1.7 Risk analysis

This study is considered to be a non-significant risk study based on United States Food and Drug administration (FDA) and International Standards Organization (ISO) guidelines due to the daily wear nature of the study. With the potential benefit of this study, the work is considered to be ethically justifiable. Ethical approval will be sought from the University of Manchester Senate Committee on the Ethics of Research on Human Beings (hereafter referred to as Manchester UREC). The work where practical will be conducted in accordance with the ICH Good Clinical Practice Guidelines and the international standard BS EN ISO 14155:2011 'Clinical investigation of medical devices for human subjects'.

Section 2. Resources

